1 STUDY SCHEME

2 STUDY SCHEDULES

Table 1:

Procedures and assessments	Screening period	Treatment period ²⁰							Follow up period		
	Day -1*	Day 1	Day 2	Day 3	Day 4	Day 5	Day 6	Day 7	Day 10 (±1 day) ¹⁶	Day 14 (± 1 day) ¹⁶	Day 28 End of Study Visit (or early termination visit) (± 1 day) ¹⁵
Informed consent	X										
Inclusion and exclusion criteria	X	X ※**									
Demographics ¹	X										
Medical history ²	X										
Randomization*		X ※*									
Treatment		X ¹⁴	X	X	X	X	X	X			
Score Assessment of WHO's 11-point scale	X	X ※**	X	X	X	X	X	X	X	X	X ¹⁹
PCR (quantitative or qualitative) ³	X	X ※**		X		X		X		X	X ¹⁷
Vital signs ⁴	X	X ※	X	X	X	X	X	X	X	X	X ^{17, 18, 19}
Physical examination ⁵	X	X ※**	X	X	X	X	X	X	X	X	X ^{17, 19}
Serum or urine pregnancy test ⁶	X										X ^{17, 19}
Clinical laboratory assessments ⁷	X	X ※**	X	X		X		X	X	X	X ^{17, 19}

	Screening period	Treatment period ²⁰							Follow up period		
Procedures and assessments	Day -1*	Day 1	Day 2	Day 3	Day 4	Day 5	Day 6	Day 7	Day 10 (±1 day) ¹⁶	Day 14 (± 1 day) ¹⁶	Day 28 End of Study Visit (or early termination visit) (± 1 day) ¹⁵
HIV/HBV/HCV Serology ⁸	X										
ECG ⁹	X	X ※**	X	X		X		X	X	X	X ^{17, 19}
Assessment of Respiratory condition ¹⁰	X	X ※**	X	X	X	X	X	X	X	X	X ¹⁷
mSOFA score	X	X ※**	X	X	X	X	X	X	X	X	X ¹⁷
Assessment of Immune function ¹¹		X ※**	X	X		X		X	X	X	X ^{17, 19}
Biomarker ¹²		X ※		X		X		X		X	X ^{17, 19}
Patient status assessment ¹³			X	X	X	X	X	X	X	X	X ¹⁷
Adverse Events		X	X	X	X	X	X	X	X	X	X
Concomitant Medication		X	X	X	X	X	X	X	X	X	X

* In case the required screening procedures take less time, randomization and start of treatment could be performed also on the same day then screening. The time period between start of screening procedures and start of treatment must not exceed 24 hours.

** Events do not need to be done if randomization is on the same day as Screening

※: prior dosing

mSOFA score: modified Sequential Organ Failure Estimated Score

¹ Demographic data: gender, age, ethnicity, height, history of allergies, history of smoking and alcohol use, weight, body mass index.

² Medical history: Medical history for the least 4 weeks.

³ If PCR was performed within 5 days before the screening visit, the test does not need to be repeated at screening and the available test results can be used.

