In the treatment period (day 1 to day 7) daily visits will be performed. If a patient will be discharged from hospital before day 7 treatment can be stopped at day of discharge. After seven days of treatment or early discharge before day 7 the follow-up (FU) period starts. Three FU visits (day 10, 14 and 28) will be conducted to assess efficacy and safety. The study assessments will be performed according to the study schedule (Table 1).

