3.4 Assignment of Analysis Sets to Analysis

The FAS serves as the primary efficacy analysis set (as randomized). All efficacy analyses are based on the FAS. The SAF will be used for the evaluation of the safety assessments (as treated) unless stated otherwise. All biomarker analyses are based on SAF (as treated) as well. The PP will only be analyzed for main efficacy outcome measures (as treated).

4 Statistical Evaluation

Continuous variables will be summarized with means, standard deviations, medians, lower and upper quartiles, minimums and maximums. Frequencies and percentages will be used to summarize categorical variables.

The two different treatment groups (groups APN01 and Placebo) will be separately tabulated. Where appropriate total columns will additionally be displayed for the two treatment groups combined.

A detailed description of the planned tables, listings and graphs is given in Appendix A.

Baseline

Baseline is defined as last observation before treatment, i.e. Day 1 value or Screening value if Day 1 value is missing or if Screening and Day 1 is the same day, unless stated otherwise.

Visit terminology

Visit No.	Notation used on the case report form	Notation used for tables, listings and graphs
10	Screening (Day -1)	Screening
150	Unscheduled visit	Screening *
20	Day 1	Day 1
30	Day 2	Day 2
40	Day 3	Day 3
50	Day 4	Day 4
60	Day 5	Day 5
70	Day 6	Day 6
80	Day 7	Day 7
150	Unscheduled visit	Day 8 *
90	FU Day 10	FU Day 10
100	FU Day 14	FU Day 14
110	FU Day 28/EOS	FU Day 28/EOS
130	FU Day 28/EOS Phone Visit	FU Day 28/EOS
170	Russia only: Home Visit FU Day 28/EOS	FU Day 28/EOS
120	Early termination	ET
140	Early termination FU Day 28/EOS	ET
150	Unscheduled visit	Unscheduled visit

ET = Early termination

** IMP administration at Screening and at Day 8 as well as all related assessments (e.g. ECG, Vital signs, etc.) are documented in eCRF as IMP administration or assessment on Unscheduled visit and will be shown in TLGs as IMP administration or assessment on Screening and Day 8 respectively.*

Unscheduled visits will not be included in any tables or graphs, only in listings and will be displayed after all scheduled visits.

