Absolute values and absolute change in PaO2/FiO2 ratio over time

The PaO2/FiO2 ratio = PaO2 [mmHg] / FiO2

This will be evaluated on each visit for ventilated patients only. If entries are not changed compared to previous entries, no entry will be done within the eCRF.

If ventilation is ongoing and/or no stop date is available, the PaO2/FiO2 ratio will be considered until date of study completion/ discontinuation or date of death respectively.

Baseline is defined as first observation of PaO2/FiO2 ratio (individual start value). Basic statistics for the PaO2/FiO2 ratio for both the absolute values and the absolute change from baseline will be tabulated by day of ventilation. Daily means will be used when more than one assessment is available per day.

Absolute values and absolute change in notified sequential organ failure assessment score (mSOFA score) over time

The mSOFA score was introduced with protocol version 5.0 and is available for patients who are included with protocol version 5.0 and higher. For patients who are included with previous protocol versions (protocol version 4.0 and lower), mSOFA score is available from the time when protocol is in effect at the centers.

Basic statistics for the mSOFA score for both the absolute values and the absolute change from baseline will be tabulated by visit.

SOFA score (protocol version 4.0 and lower) will be listed only.

Time to a 2-point decrease in WHO's 11-Point Score system

Time to 2-point decrease [days] = Assessment date of first ≥ 2 improvement - Date of randomization.

Patients without documented 2-point decrease who completed the study or was early terminated or discharged from hospital before Day 28 will be censored at the date of last WHO assessment available.

Time to 2-point decrease will be analyzed using Kaplan-Meier estimates and plots, log-rank test, and Cox proportional hazards model (adjusted for center and age to derive hazard ratios and corresponding 95% confidence intervals).

Kaplan-Meier estimates and Log-rank test

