Kaplan-Meier table (product-limit "survival" estimates with 95%-CI, Standard error, Number of patient with event, Number of patient at risk) for Time to 2-point decrease [days], Kaplan-Meier Summaries of Event/Censoring (Number of patient with event, Number of patient censored, Total number of patients), Quartile Estimates (Median Time to Event, 1st Quartile, 3rd Quartile, 95%-CI) and Kaplan-Meier table ("survival" estimates with 95%-CI) for Timepoint (28 days). Time to 2-point decrease [days] will be displayed by a Kaplan-Meier-curve. Treatments groups will be compared with Log-rank test.

Cox proportional hazards model

The hazards ratio along with its associated 95% confidence intervals as well as parameter estimate and p-value (two-sided) will be reported.

Absolute values and absolute change in lymphocyte counts over time

Results of lymphocyte counts will be converted to standard unit before any calculation if needed. Conversion of all lab values will be described in a separate document.

Basic statistics for both the absolute values and the absolute change from baseline will be tabulated by visit.

Absolute values and absolute change in C-reactive protein levels over time

Results of C-reactive protein will be converted to standard unit before any calculation if needed. Conversion of all lab values will be described in a separate document.

Basic statistics for both the absolute values and the absolute change from baseline will be tabulated by visit.

Absolute values and absolute change in D-dimer over time

Results of CD-dimmer will be converted to standard unit before any calculation if needed. Conversion of all lab values will be described in a separate document.

Basic statistics for both the absolute values and the absolute change from baseline will be tabulated by visit.

Absolute values and absolute change in log transformed levels of LDH over time

Results of LDH will be converted to standard unit before any calculation if needed. Conversion of all lab values will be described in a separate document. Standardized results will be log transformed for this endpoint.

Basic statistics for both the absolute values and the absolute change from baseline will be tabulated by visit.

Time to hospital discharge

Time to hospital discharge [days] will be calculated as Date discharge from hospital - Date of randomization.

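### Time to a 2-point WHO improvement is dated or censored by a sparse visit calendar after Day 7, while the recorded discharge date, which itself shows improvement for most baselines, goes unused

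*Protocol*

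**What the plan says.** **Schedule.** In Protocol section 2, Table 1, the row "Score Assessment of WHO's 11-point scale" is marked at screening, on each of Days 1 to 7, and on Days 10, 14 and 28, the last three with a window of ±1 day. Protocol 8.1 agrees: "Three FU visits (day 10, 14 and 28) will be conducted to assess efficacy and safety". No score is planned between Day 14 and Day 28. Extra visits are not planned to fill the gap; the visit terminology part of SAP section 4 says "Unscheduled visits will not be included in any tables or graphs, only in listings".

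**Event and censoring.** SAP 4.4.2 sets time to a 2-point decrease as "Assessment date of first ≥ 2 improvement - Date of randomization". Patients without a documented decrease, including those who complete, stop early or are discharged, "will be censored at the date of last WHO assessment available".

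**Analysis.** "Time to 2-point decrease will be analyzed using Kaplan-Meier estimates and plots, log-rank test, and Cox proportional hazards model". The output includes "Quartile Estimates (Median Time to Event, 1st Quartile, 3rd Quartile, 95%-CI") and a 28-day Kaplan-Meier value. The SAP names neither an interval-censored method nor a rule for ties.

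**Discharge.** Another endpoint in SAP 4.4.2 is computed as "Date discharge from hospital - Date of randomization", so the date is in the database. It plays no part in the WHO endpoint.

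**Status.** Protocol 8.7.1.2.5 makes the secondary endpoints descriptive and exploratory.

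**The concern.** After Day 7 the date of improvement is known only to lie between two assessments, yet it is analysed as an exact time. Two things follow.

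- Medians, quartiles and the curve between visits can reflect when patients were seen rather than when they improved.
- The censoring rule can remove patients because they recovered. Going home is the clearest improvement in this population. For most baselines it satisfies the 2-point definition, but a discharged patient who is not rescored leaves the analysis as not improved.

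For an exploratory phase II endpoint, the median and the curve are what readers take away. These are the outputs affected.

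**Working it through.** **1. The plan's own figures.** The documents give no expected median, effect or power for this endpoint. The only power statement concerns the primary composite. With 50% v 30%, two-sided 0.05 and 80% power, n = [1.96·√(2·0.4·0.6) + 0.8416·√(0.25 + 0.21)]² / 0.2² = (1.358 + 0.571)² / 0.04 ≈ 93 per group, or 186 in total. That agrees with the plan and is not touched by this point.

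**2. What discharge means on the scale (Annex 1).** Hospitalised states start at 4; ambulatory states are 1 to 3.
- Baseline 4: discharge guarantees only 4 − 3 = 1 point.
- Baseline 5: discharge gives at least 5 − 3 = 2 points. Score 3 or less is ambulatory, so apart from the note on hospitalisation for isolation only, the improvement occurs at discharge.
- Baseline 6 or more: discharge gives at least 3 points, but an earlier in-hospital fall (6 to 4, say) may already have qualified. Discharge is then the latest possible date.

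**3. One patient.** Baseline 5, randomised on Day 1, seen on Day 14, home on Day 15. The time to improvement is 15 − 1 = 14 days.
- Rescored on Day 28: recorded as 28 − 1 = 27 days, 13 days late.
- Not rescored: censored at 14 − 1 = 13 days as not improved.

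The second path is realistic. The SAP's responder rule lists discharge and in-home visits among the reasons for a missing WHO score. Table 1 footnote 19, attached to the Day 28 WHO cell, does not include the score in its list of home assessments.

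**4. Direction of the censoring error.** Suppose n patients are at risk after one visit, d are discharged alive (all baseline 5 or more) before the next, a share f of these is not rescored, and nobody else improves. The true proportion improving is d/n. The Kaplan-Meier step is (1 − f)d / (n − fd). This equals d/n at f = 0, is smaller for any f above 0 when d < n, and is 0 at f = 1. The documents do not allow f to be estimated.

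**5. Medians on nominal visit days.** With full attendance the reported median is the first visit on or after the true median.

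| True median (study day) | Reported |
|---|---|
| above 7 to 10 | 10 |
| above 10 to 14 | 14 |
| above 14 to 28 | 28 |

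- True 12 v 14.5 (2.5 days apart): reported 14 v 28, or 14 days.
- True 15 v 24 (9 days apart): reported 28 v 28, or 0 days.

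A 2.5-day difference straddles Day 14 only if the faster median is beyond Day 11.5.

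**6. Sampling error and visit windows.** Simulation under assumptions: Weibull times with shape 1.5, full attendance, no deaths, windows spread evenly over ±1 day.

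| True medians | 100 per arm, nominal days | 100 per arm, ±1 day | 5,000 per arm, ±1 day |
|---|---|---|---|
| 12 v 14.5 | 14 days in 54%, 0 in 41% | 12-14 days in 56%, 0-2 in 37% | 12-13 days |
| 15 v 24 | 0 days in 70%, 14 in 26%; slower median not reached in 4% | 0-2 days in 72%, 13-14 in 27% | 1-2 days |

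**7. How many and how late.** Assume exponential times with median 12 days after randomisation, full attendance and visits at 13 and 27 days. S(13) = 2^(−13/12) = 0.472 and S(27) = 2^(−27/12) = 0.210. The share of improvements by Day 28 that fall in the last gap is (0.472 − 0.210) / (1 − 0.210) = 33%. They are dated 7.9 days late on average.

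**8. Tests and hazard ratio.** Assume exponential medians of 16 v 12 days, 100 per arm, full attendance. The mean hazard ratio is 1.34 with exact times; with visit dates it is 1.29 under Breslow ties and 1.34 under Efron ties. Log-rank power lies between 0.40 and 0.45 across the runs and changes by at most 0.02 between exact and visit dating.

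**The case against.** The case for leaving the plan alone has force.

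- **The comparison hardly moves.** Both arms share one schedule. The log-rank test stays valid under the null, and with Efron ties the hazard ratio is unchanged. This stands for full attendance. The effect of missing rescoring on power was not quantified.
- **The curve is right at the visits.** With complete visits, Kaplan-Meier on visit dates equals the Turnbull estimate at each visit, including Day 28. This stands. The fault is between visits and where discharged patients are not rescored.
- **The examples are chosen.** Through Day 7 the rounding is at most one day, and no expected median is given. This stands. A reader might infer that the trial will report exactly 14 days or exactly zero in such cases. The documents do not support that: those are nominal-day figures, the windows soften them to about 13 and 1-2 days, and they appear in roughly half to three-quarters of simulated trials.
- **Late dating at Day 28 is not certain.** A reader might infer that everyone who improves after Day 14 is dated Day 28. Under the censoring rule, someone discharged and not rescored is censored at the last score instead. The 33% and 7.9 days in step 7 therefore assume full attendance.
- **Turnbull cannot place a median inside Days 14-28.** This also stands. A parametric interval-censored Weibull fit recovered about 2.5 and 9.0 days, but the simulated data were Weibull. Discharge dates are what add information in the gap.
- **Other endpoints cover it.** Responder proportions use the visit grid, and time to discharge uses exact dates. This stands only in part: the responder rule counts unassessed discharged patients as non-responders.

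**Conclusion.** The point holds as a weakness in how one exploratory secondary endpoint is estimated and displayed. Improvements between visits are dated up to about 14 days late. Patients with baseline 5 or more who are discharged alive and not rescored are censored as not improved, against the plan's own scale and despite a recorded date. If medians or quartiles lie beyond about Day 11, which is an assumption, a 2.5-day difference straddling Day 14 can be reported as about 13-14 days and a 9-day difference inside Days 14-28 as about 0-2.

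A reader might go further and infer an inflated type I error or a compromised trial result. The documents do not support this: the schedule is common to both arms, and the primary endpoint and its sample size are unaffected. The discharge argument takes discharge alive to mean an ambulatory state under Annex 1, not transfer to another hospital.

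**What to change.** In SAP 4.4.2, time to a 2-point decrease:

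- **(a) Use discharge.** For patients with baseline 5 or more discharged alive with no earlier documented 2-point improvement, count discharge as the improvement instead of censoring or waiting for the next visit. For baseline 5, the discharge date is the event date. For baseline 6 or more, it is the upper limit of an interval starting at the last assessment without improvement.
- **(b) Handle the rest as intervals.** Use a Turnbull curve, with the median given as an interval where it is not identifiable, and an interval-censored or grouped proportional hazards model. The minimum alternative is to specify Efron ties and state with the results that medians after Day 7 are known only to the visit interval.
- **(c) Keep the current analysis** as a sensitivity analysis.

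Protocol 8.7.1.2.5 also censors at the last WHO evaluation, so list the change in SAP section 5 and make it before unblinding.

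**Cost.** SAP wording and different programming for one endpoint; no new data. Some medians become intervals. Discharge as an inspection time depends on recovery, which strains the usual independence assumption for interval-censored data; the SAP should say so.

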⁴ Vital signs include temperature, heart rate, respiration, blood pressure, and oxygen saturation. Vital signs need to be tested before and after each dose (within 30 min before/after IMP administration).

⁵ physical examination could also be documented in the context of the general visit/health status assessment e.g. during a general clinical review

⁶ Pregnancy Test: for FOCP only

⁷ Laboratory tests include the following: in case a local lab cannot perform any of these parameters it should be reported as missing value

- Inflammatory indicators: C- reactive protein (CRP), erythrocyte sedimentation rate (ESR), and procalcitonin.
- Blood routines include: red blood cell (RBC) count, hematocrit (HCT) or hematocrit total, and classification of white blood cells (WBC), hemoglobin (Hb), platelet (PLT) count.
- Urine routine includes: glucose (GLU), pH (PH), urinary protein (PRO), red blood cells (BLD), and white blood cells (LEU).
- Stool routine + occult blood: red blood cells (BLD), white blood cells (LEU), occult blood.
- Blood biochemistry includes: aspartate aminotransferase (AST), alanine aminotransferase (ALT), alkaline phosphatase (AKP), total bilirubin (TBI), total protein (ALB), albumin (ALB), urea nitrogen (BUN), Creatinine (Cr), uric acid (UA), potassium (K), sodium (Na), eGFR (assessment is calculated according to the formula used in local laboratory).
- Myocardial enzymes: creatine kinase (CK) and isoenzyme (CKMB), lactate dehydrogenase (of LDH), [alpha] - hydroxybutyrate dehydrogenase ([alpha] - HBD), troponin (of cTnI).
- Coagulation functions include: prothrombin time (PT), activated partial thromboplastin time (APTT), D- dimer, FIB

⁸ results do not need to be available before randomization, results up to 4 weeks old are acceptable

⁹ 12- lead ECG: within 30 min after IMP administration

¹⁰ Respiration: blood gas analysis (oxygenation index, blood lactic acid) or pulse oximetry.

¹¹ Immune function: immunoglobulin (Ig A, Ig M, Ig G)

¹² Biomarkers comprising (per collection of whole blood 10-12 ml)

1 Li-Heparin blood collection tube (5-6 ml):

1. Plasma equilibrium angiotensin levels: Angiotensin II (Ang II), Angiotensin 1-7 (Ang. 1 -7), Angiotensin 1-5 (Ang 1-5), Angiotensin I (Ang I), Angiotensin 1-9 (Ang 1-9)
2. Aldosterone
3. ACE2 Activity and ACE2 concentration
4. Other exploratory RAAS Biomarkers indicators: specific exploratory indicators will be determined as needed

1 EDTA blood collection tube (5-6 ml):

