8.5.2 Appropriateness of Measurements

8.5.2.1 Screening Procedures

Written, signed, and dated informed consent from the patients prior to the performance of any clinical trial related procedures must be obtained by an investigator. A copy of the signed consent form and the information sheet must be given to the patient for their records after signature and before enrollment.

The time period between start of screening procedures and start of treatment must not exceed 24 hours. In case the required screening procedures take less time, randomization and start of treatment could be performed also on the same day then screening. Pre-dose events other than biomarker sampling and vital signs do not need to be performed if randomization and screening are on the same day. The following events will be performed: check of inclusion and exclusion criteria, obtaining medical history and demographics, score assessment of WHO's 11-point scale, PCR analysis, vital signs, physical examination, serum or urine pregnancy test, lab assessments, ECG, assessment of respiratory condition, mSOFA-score.

See Table 1 for a complete list of screening procedures to be performed.

Only an authorized and trained investigator may decide on the eligibility of the patient.

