To assess the immune function the following parameter will be analyzed:

COVID-19 Antibodies

Immunoglobulin (IgG, IgA, IgM)

Serology

During the screening period only, 1 or 2 blood samples will be drawn to test for the presence of HIV, HBsAg, and HCV antibody.

HIV testing (HIV I and HIV II) HCV antibody screen

HBV testing (HBsAg)

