4.6 Biomarker Analysis

All continuous results of laboratory data will be converted to standard unit before any calculation if needed. Conversion of all lab values will be described in a separate document.

No statistical testing procedures will be applied to Biomarker analyses.

Absolute values as well as absolute change from baseline for the following biomarker data will be analyzed by visit using basic statistics:

- Li-Heparin blood collection tube (5-6 ml):
 - Plasma equilibrium angiotensin levels: Angiotensin II (Ang II), Angiotensin 1-7 (Ang 1-7), Angiotensin 1-5 (Ang 1-5), Angiotensin I (Ang I), Angiotensin 1-9 (Ang 1-9)
 - NT-proBNP, Ferritin
 - Aldosterone
 - Angiotensin-converting enzyme 2 (ACE2) activity and concentration
- EDTA blood collection tube (5-6 ml):
 - Plasma-Renin-Concentration (PRC)

- Cytokines: Interleukin 6 (IL-6), Interleukin 8 (IL-8), soluble tumor necrosis factor receptor type II (TNFR-II), Plasminogen activator inhibitor type-1 (PAI-1), von Willebrand factor (vWF-A2), Tumor necrosis factor- α (TNF- α)
- Alveolar epithelial markers: Soluble receptor for advanced glycation end products (RAGE), Surfactant protein-D (SP-D)
- Endothelial markers: Angiopoietin-2
- Immune function and COVID-19 antibodies: Immunoglobulin A (IgA), Immunoglobulin G (IgG) and Immunoglobulin M (IgM), Anti-SARS-CoV-2 antibody

Serology

The proportion of patients with positive or negative test results for HIV, Hepatitis B and Hepatitis C will be tabulated.

All serology data will be listed as well.

Clinical laboratory markers associated with poor outcome over time

Clinical laboratory markers associated with poor outcome (e.g., lymphocyte counts, D-Dimer, CRP) is a part of safety analysis (clinical laboratory assessments) and secondary endpoints. Absolute values as well as absolute change from baseline for this endpoint will be presented together with other clinical laboratory assessments.

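### The same-day waiver lets sites skip the only scheduled pre-treatment immune-function sample, so some patients may have no immunoglobulin baseline for a descriptive SAP item

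*Protocol*

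**What the plan says.** In Protocol Section 2, Table 1, the row "Assessment of Immune function" has an empty Screening cell. Its Day 1 cell is marked as pre-dose and with **. Samples follow on Days 2, 3, 5, 7, 10, 14 and 28. Footnote 11 defines the content as IgA, IgM and IgG. Footnote ** reads: "Events do not need to be done if randomization is on the same day as Screening".

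Protocol Section 8.5.2.1 repeats the rule: "Pre-dose events other than biomarker sampling and vital signs do not need to be performed if randomization and screening are on the same day". Its list of screening procedures names no immune-function sample. It ends: "serum or urine pregnancy test, lab assessments, ECG, assessment of respiratory condition, mSOFA-score".

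The SAP (Section 4, Baseline) takes the last observation before treatment, which it spells out as "Day 1 value or Screening value if Day 1 value is missing or if Screening and Day 1 is the same day". SAP 4.6 then says: "Absolute values as well as absolute change from baseline for the following biomarker data will be analyzed by visit using basic statistics". The list that follows includes IgA, IgG, IgM and anti-SARS-CoV-2 antibody. SAP 4.7 rules out imputation, and SAP 4.6 rules out statistical testing of biomarkers.

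COVID-19 antibodies have no single home. Table 1 footnote 12 puts them in the EDTA biomarker tube. Section 8.5.2.2.6 puts them with the immunoglobulins, under the line "To assess the immune function the following parameter will be analyzed". The biomarker list in Section 8.5.2.2.7 omits them.

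**The concern.** A same-day waiver is harmless when it only avoids repeating something done a few hours earlier at Screening. For immune function there is nothing earlier to repeat, so the waiver can remove the only scheduled value before study drug. The SAP's fallback then points to a Screening value that the schedule never asks for.

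Same-day entry is a planned route. Treatment must start within 24 hours of the start of screening, randomisation may fall on Day -1, and the first dose may be given that evening. The trigger is the day of randomisation, so a patient randomised on Day -1 and first dosed on Day 1 is covered as well.

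At stake is the change-from-baseline summary for the immunoglobulins and, under one of the two placements, for the antibodies. A pre-treatment sample that was not taken cannot be recovered later.

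**Working it through.** **1. Which rows rely on the waiver.** Reading Table 1 row by row, nine rows carry ** on Day 1:

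| Row marked ** on Day 1 | Screening assessment? |
|---|---|
| Inclusion and exclusion criteria | Yes |
| WHO 11-point scale | Yes |
| PCR | Yes |
| Physical examination | Yes |
| Clinical laboratory | Yes |
| ECG | Yes |
| Respiratory condition | Yes |
| mSOFA | Yes |
| Immune function | **No** |

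The biomarker row also has no Screening sample, but its Day 1 cell carries no **, so its pre-dose draw is kept for everyone. The protocol therefore already protects the adjacent row that has the same feature.

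**2. What follows for one patient.** For a patient randomised on the screening day whose site uses the waiver:
- Scheduled pre-treatment immunoglobulin values: Screening 0 + Day 1 0 = 0.
- First scheduled value: Day 2, after dosing.
- SAP baseline: the Day 1 value is missing and the Screening value is not scheduled, so there is none.
- Change from baseline with no imputation: cannot be calculated at any visit. The absolute values at later visits remain.

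**3. How many patients.** The plan gives no figure for this. Inputs: N = 200 enrolled (Protocol 8.7.2); s = share randomised on the screening day, which the documents do not give and is assumed here; full uptake of the waiver, also assumed. Number without a baseline = N × s.

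| Assumed s | Without baseline | With baseline |
|---|---|---|
| 25% | 200 × 0.25 = 50 | 150 |
| 50% | 200 × 0.50 = 100 | 100 |
| 75% | 200 × 0.75 = 150 | 50 |

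These are upper figures for each s. Any site that still draws the sample lowers them.

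**4. Antibodies.** Under footnote 12 they belong to the biomarker row, which is not waived, so the baseline is kept. Under Section 8.5.2.2.6 they belong to immune function, so the baseline can be skipped. The two sections lead to different collection for the same patient.

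**5. What is not affected.** The sample size (93 per group, 186 in total, 80% power for 50% versus 30%) reproduces with a chi-squared calculation without continuity correction. It uses none of these values.

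**The case against.** Several points on the other side have weight.

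- **The waiver is permissive.** It does not forbid the sample, and the SAP would accept any observation taken before treatment. A reader might infer that every same-day patient is certain to drop out of the change analysis. The documents do not support that; it happens only where the sample is not drawn.
- **Other text could be read as rescuing the sample.** Section 8.5.2.2 asks for Day -1/1 assessments before dosing, but this can be read as governing timing only. Section 8.5.2.2.6 places immune function under clinical laboratory assessments, and the screening list includes laboratory assessments. Against that, Table 1 gives immune function its own row, and footnote 7, which defines the laboratory tests, omits immunoglobulins. The SAP classes immune function as a biomarker item, but Table 1 separates the two rows and puts ** on one only. The Laboratory Manual may settle the matter; it is not among the documents reviewed.
- **The item is minor.** Immunoglobulins and COVID-19 antibodies are not in the protocol's biomarker endpoint lists (Sections 7.2.1 and 8.7.1.2.6). They appear as endpoints only in SAP 2.4 and 4.6. This stands.
- **No comparison is planned.** A reader might infer a loss of precision in an arm difference and its confidence interval. SAP 4.6 and 4.9 plan basic statistics only, with no test and no interval for these variables, so there is no planned comparison to weaken.
- **No bias between arms is shown.** A reader might infer bias because site logistics decide who is same-day. The day of randomisation is fixed before treatment, the trial is double-blind, and center is a randomisation factor, so the loss should not differ by arm.

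The mismatch between the waiver and the empty Screening cell survives all of these.

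**Conclusion.** The point holds as a schedule inconsistency with a limited effect. Immune function is the only waivable Day 1 row with no Screening assessment, and the SAP baseline rule does not fill the gap. Where the waiver is used, the patient is lost from the change-from-baseline summary of IgA, IgM and IgG.

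The size depends on two unknowns: the same-day share and how often sites use the waiver. The range of 50 to 150 patients rests on an assumed share of 25% to 75% with full uptake.

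The consequence is a descriptive summary based on fewer and less representative patients. The primary endpoint, the power and the later absolute values are unaffected. It would go too far to say that baseline antibody status is generally lost: that arises only where a site follows Section 8.5.2.2.6 instead of Table 1 footnote 12.

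**What to change.** Three edits to the protocol:

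1. Remove ** from the Day 1 immune-function cell in Table 1.
2. In Section 8.5.2.1, add immune function to the items that must still be done before dosing when screening and randomisation fall on the same day, alongside biomarker sampling and vital signs.
3. List COVID-19 antibodies in one place only, and make Table 1 and Sections 8.5.2.2.6 and 8.5.2.2.7 agree.

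The blood can be taken at the Day 1 pre-dose biomarker draw, which is already required of every patient. The cost is one symbol, a few words and a few mL more blood for same-day patients. No change to the SAP baseline rule is needed, because a Day 1 pre-dose value would then be scheduled for everyone.
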